There were no deaths reported during MG0002. One subject (2.3%) discontinued from the study due to an AE (MG crisis). In addition, 3 subjects experienced TEAEs (headache) that led to discontinuation of IMP, but the subjects remained in the study. Six subjects (14.0%) reported a total of 7 serious TEAEs. One subject in the Placebo-Rozanolixizumab [REDACTED] Group experienced a serious TEAE of headache that was considered by the investigator to be related to the IMP. With the exception of 1 serious TEAE of ulna fracture, all other serious TEAEs were in the System Organ Class of Nervous system disorders. Three subjects (7.0%) reported serious TEAEs of MG (the studied indication), and 1 subject (2.3%) reported a serious TEAE of MG crisis. The most common TEAEs were headache (23 subjects [53.5%]), diarrhea (11 subjects [25.6%]), and nausea (6 subjects [14.0%]). Overall, repeated administrations of rozanolixizumab at dose levels of [REDACTED] and [REDACTED] were generally [REDACTED] and well tolerated, with an acceptable safety profile.

The underlying hypothesis of the current study is that reducing the concentration of pathogenic IgG in patients with CIDP will improve the symptoms of CIDP and prevent long-term progression. Thus, rozanolixizumab may provide an important novel therapeutic approach to address the need for effective treatment of CIDP.

The current study, CIDP01, will assess the effectiveness of treatment with a weekly dosing regimen of rozanolixizumab for 12 weeks (dosing at Visits 2, 4, 6, and Visits 8 through 16) in subjects with active CIDP who have been maintained on an immunoglobulin-dependent regimen. In addition, this study will assess the safety and tolerability of multiple dosing with rozanolixizumab including the development of [REDACTED] and potential to impact clinical response, and will provide information on the PK and PD of rozanolixizumab in subjects with active CIDP.

Additional information on the development of rozanolixizumab can be found in the current version of the IB for rozanolixizumab.

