#### **4.1.2 Other efficacy variables**

Preliminary definitions linked to assessment of relapse:

- **CIDP relapse (iRODS)** is defined as a clinically important deterioration from Baseline in iRODS score, ie, a MCID-SE of  $\leq -1.96$
- **CIDP relapse (adjusted INCAT)** is defined as an increase from Baseline of at least 1 point in the adjusted INCAT score. The adjusted score is identical to the INCAT disability score except for the exclusion of changes in upper limb function from 0 (normal) to 1 (minor symptoms) or from 1 to 0
- **CIDP relapse (maximum grip strength as assessed by site personnel)** is defined as a clinically important deterioration from Baseline in grip strength as measured by site personnel, ie, a decline of  $>14\text{kPa}$

Other efficacy variables will include:

- Subject experienced **CIDP relapse (iRODS)** up to Week 13 (Day 85) after first treatment

- Time to **CIDP relapse (iRODS)** during the Treatment Period
- Values and change from Baseline in iRODS scores at each scheduled assessment during the Treatment and Observation Periods
- Subject experienced **CIDP relapse (adjusted INCAT)** up to Week 13 (Day 85) after first treatment
- Time to **CIDP relapse (adjusted INCAT)** during the Treatment Period
- Values and change from Baseline in adjusted INCAT score at each scheduled assessment during the Treatment and Observation Periods
- Subject experienced **CIDP relapse (maximum grip strength as assessed by site personnel)** up to Week 13 (Day 85) after first treatment
- Time to **CIDP relapse (maximum grip strength as assessed by site personnel)** during the Treatment Period
- Values and change from Baseline in maximum grip strength score (maximum of 3 assessments) taken by site personnel at each scheduled assessment during the Treatment and Observation Periods
- Values and change from Baseline in daily maximum grip strength score (maximum of 3 assessments) taken by the subject at the same time each day during the Treatment and Observation Periods
- Values and change from Baseline in RT-MRC sum score at each scheduled assessment during the Treatment and Observation Periods
- Values and change from Baseline in fatigue at each scheduled assessment during the Treatment and Observation Periods
- Values and change from Baseline in CIDP PRO instrument at each scheduled assessment during the Treatment and Observation Periods

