## **12 ASSESSMENT OF SAFETY**

### **12.1 Adverse events**

#### **12.1.1 Definitions**

##### **12.1.1.1 Adverse event**

An AE is any untoward medical occurrence in a patient or clinical investigation subject administered a pharmaceutical product that does not necessarily have a causal relationship with this treatment. An AE can therefore be any unfavorable and unintended sign (including an abnormal laboratory finding), symptom, or disease temporally associated with the use of a medicinal (investigational) product, whether or not related to the medicinal (investigational) product.

In order to ensure complete safety data collection, all AEs occurring during the study (ie, after the signing of the Informed Consent form), including any pretreatment and posttreatment periods required by the protocol, must be reported in the eCRF even if no IMP was taken but specific study procedures were conducted. This includes all AEs not present prior to the initial visit and all AEs that recurred or worsened after the initial visit.

Signs or symptoms of the condition/disease for which the IMP is being studied should be recorded as AEs only if their nature changes considerably or their frequency or intensity increases in a clinically significant manner as compared to the clinical profile known to the investigator from the subject's history or the Baseline Period.

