#### **12.1.1.2.1 Anticipated serious adverse events**

The following Anticipated SAEs are anticipated to occur in the population studied in this protocol at some frequency that is independent of drug exposure.

This list does not change the investigator's obligation to report all SAEs (including Anticipated SAEs) as detailed in Section 12.1.2.3.

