**Table 12-1: Anticipated serious adverse events for CIDP population**

Neurologic diseases a :	muscle weakness, numbness and pain in the extremities, impaired balance, difficulty walking
------------------------------------	---

a The investigator should report these adverse events as serious adverse events only if they meet criteria for seriousness (see Section 12.1.1.2).

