## 10.2 Adverse events

Adverse events will be recorded from the time of informed consent until study completion. All AEs will be coded (Section 3.8) and categorized by relationship to rozanolixizumab.

In addition, AEs will be classified according to the Common Terminology Criteria for Adverse Events (CTCAE) Version 5.0 for severity. For any AEs where it is not possible to provide a CTCAE grading, the events will be assessed using a standard intensity classification (mild, moderate and severe).

A TEAE is defined as any event that was not present prior the first administration of IMP or any unresolved event already present before the first administration of IMP that worsens in intensity following exposure to treatment until 8 weeks following the last administration of IMP. Adverse events starting before the first administration of IMP or later than 8 weeks after the administration of the last IMP will not be considered TEAEs. Such events will be listed only.

Where dates are missing or partially missing, AEs will be assumed to be treatment-emergent unless evidence exists that does not allow the AE to be treatment-emergent. Handling of missing dates/times for classification of AEs as TEAEs is described in Section 4.2.7.

The following rules will be used to assign a TEAE to the study periods:

1. **Treatment Period:** a TEAE will be assigned to the Treatment Period for the tabulations if the start date/time of the event is at the time of or after the first administration of IMP on Day 1, up to Visit 17/PEOT (non-inclusively).
2. **Observation Period:** a TEAE will be assigned to the Observation Period for the tabulations if the start date/time of the event is at or after Visit 17/PEOT till 8 weeks after administration of the last IMP.
  - The Observation Period's TEAEs will be stratified by TEAEs of participants who received/did not receive standard of care treatment (i.e. Ig treatment) between start of the Observation Period and occurrence of the TEAE.

The number and percentage of participants who experience TEAEs will be summarized by Treatment Period, Observation Period (standard of care treatment status identified by WHODD J06BA01 and J06BA02) and Overall with respective treatment group. The following summaries will be presented:

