- Incidence of TEAEs (overview including number and percentage of participants with any TEAEs, serious TEAEs, discontinuations due to TEAEs, related TEAEs, TEAEs with CTCAE Grade 3 and above [or rated as 'severe' for events with no CTCAE classification], and deaths; event counts will also be included)
- Incidence of TEAEs by SOC, HLT and PT
- Incidence of TEAEs during the Dosing Period by SOC, HLT and PT
- Incidence of serious TEAEs by SOC, HLT and PT
- Incidence of non-serious TEAEs by SOC, HLT and PT
- Incidence of AEs of special interest by SOC, HLT and PT
- Incidence of AEs of interest by SOC, HLT and PT

- Incidence of TEAEs by relationship, SOC, HLT and PT
- Incidence of TEAEs by maximum relationship, SOC, HLT and PT
- Incidence of serious TEAEs by relationship, SOC, HLT and PT
- Incidence of non-serious TEAEs by relationship, SOC, HLT and PT
- Incidence of fatal TEAEs by relationship, SOC, HLT and PT
- Incidence of TEAEs by maximum intensity (mild, moderate and severe), SOC, HLT and PT
- Incidence of non-serious TEAEs above threshold of 5% of participants by SOC and PT
- Incidence of non-serious TEAEs above threshold of 5% of participants by relationship, SOC and PT
- Discontinuation due to AEs

Summary tables will contain counts of participants, percentages of participants in parentheses and the number of events. A participant who has multiple events in the same SOC, HLT and PT will be counted only once in the participant counts but all events will be included.

Adverse event summaries will be ordered by alphabetical SOC, alphabetical HLT within SOC and decreasing frequency in the active treatment group.

In summaries including intensity, the CTCAE categories will be summarized according to the following categories:

- Grade 1: Mild
- Grade 2: Moderate
- Grade 3: Severe
- Grade 4: Severe
- Grade 5: Severe
- not gradable

In the case both category types are captured and the mapping to a standard intensity classification per above rule results in a class different from the standard intensity classification given in the eCRF, the worst case will be used.

These will be tabulated together with the AEs that were not classified according to CTCAE criteria i.e., all Grade 1 AEs as per CTCAE criteria will be included in the 'mild' category together with those AEs classified as mild as per the 'standard' intensity classification.

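### CIDP worsening recorded as an adverse event is pooled with toxicity in the SAP's TEAE overview rows, so an excess of placebo relapses could dilute or reverse a toxicity difference in those rows

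*SAP*

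**What the plan says.** **Recording rule.** Protocol 12.1.1.1: "Signs or symptoms of the condition/disease for which the IMP is being studied should be recorded as AEs only if their nature changes considerably", or if "their frequency or intensity increases in a clinically significant manner as compared to the clinical profile known to the investigator". The comparison profile comes from the subject's history or the Baseline Period. Relapse is not exempted.

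**Anticipated SAEs.** Protocol Table 12-1 names "muscle weakness, numbness and pain in the extremities, impaired balance, difficulty walking". Protocol 12.1.1.2.1 describes such events as "anticipated to occur in the population studied in this protocol at some frequency that is independent of drug exposure". They are still reported when they meet a seriousness criterion.

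**Relapse.** In Protocol 4.1.2 an iRODS relapse "is defined as a clinically important deterioration from Baseline in iRODS score". The grip-strength definition is worded in the same way. The adjusted INCAT definition requires only a rise of at least 1 point.

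**TEAEs.** SAP 10.2 counts new events and any unresolved earlier event "that worsens in intensity following exposure to treatment until 8 weeks following the last administration of IMP". It has no carve-out for CIDP. The first planned summary is an "overview including number and percentage of participants with any TEAEs, serious TEAEs, discontinuations due to TEAEs, related TEAEs", with further rows for Grade 3 and above and for deaths. None of these rows has a version without CIDP terms.

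**Why the rows matter.** The first two safety variables in Protocol 4.2.6 and SAP 2.2.4 are the occurrence of TEAEs and TEAEs that lead to IMP withdrawal. They serve the secondary safety and tolerability objective.

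**Design.** Inclusion criterion 5 requires documented Ig dependency. Protocol 7.7.2 prohibits IVIg and SCIg during the Treatment Period. Protocol 6.4 makes relapse or rescue a reason to stop IMP.

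**Other planned outputs.** SAP 10.2 also plans tables by SOC, HLT and PT, by relationship and by intensity; AE-of-focus tables for named toxicities; a flagged listing by arm and participant; and, for the Observation Period only, a split by Ig treatment.

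**The concern.** A pooled TEAE count normally stands for harm. Here it can also contain failure of efficacy. A relapse that satisfies the recording rule adds a placebo participant to the same row in which a severe headache adds a rozanolixizumab participant. If the drug prevents relapses, the row falls on the active arm for reasons unrelated to tolerability. A true excess of toxicity could then look small, absent or reversed in the rows closest to the named safety variables. The planned Ig-status split does not help, because a relapse that starts before the PEOT Visit falls in the Treatment Period.

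**Working it through.** **Does CIDP worsening reach the rows?** Take the provisions in order. The recording rule admits a clinically significant increase and does not exempt relapse. The TEAE definition removes no CIDP term, and neither does any overview row. Worsening that meets the rule is therefore counted as any TEAE, as serious or Grade 3 and above if graded so, and as a discontinuation if the stop is attributed to the AE.

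**Programme precedent.** The Introduction says of MG0002: "Three subjects (7.0%) reported serious TEAEs of MG (the studied indication), and 1 subject (2.3%) reported a serious TEAE of MG crisis". The percentages reproduce: 3/43 = 7.0% and 1/43 = 2.3%. MG and MG crisis are separate terms, so at least 3 + 1 = 4 of the 7 serious TEAEs were the studied disease. The one AE-related study discontinuation was MG crisis, but three subjects stopped IMP for headache. Both kinds of event were therefore counted as TEAEs. No split by arm is given.

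**How far could a row move?** The documents give no TEAE or relapse rate by arm, so there is no planned figure to reproduce. The sample size contributes only the scale: 34 randomized 1:1 is 17 per arm, so one participant is 1/17 = 5.9 points.

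Let t be the proportion with a non-CIDP (toxicity) event and c the proportion with recorded CIDP worsening. If the two are assumed independent, the pooled row is

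P = 1 - (1 - t)(1 - c).

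Two examples with toxicity 40% on rozanolixizumab and 10% on placebo:

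- CIDP 10%/30%: 1 - 0.60 × 0.90 = 46%, against 1 - 0.90 × 0.70 = 37%. The difference is +9 points.
- CIDP 10%/50%: 46%, against 1 - 0.90 × 0.50 = 55%. The difference is -9 points.

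The full grid follows. All rates are assumed, each pair is rozanolixizumab/placebo, and cells are the pooled difference in points:

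| Recorded CIDP worsening | Toxicity 20%/5% (true +15) | Toxicity 40%/10% (true +30) | Toxicity 60%/30% (true +30) |
|---|---|---|---|
| 30%/30% | +10.5 | +21 | +21 |
| 10%/30% | -5.5 | +9 | +13 |
| 20%/50% | -16.5 | -3 | +3 |
| 10%/50% | -24.5 | -9 | -1 |
| 10%/60% | -34 | -18 | -8 |

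With equal CIDP rates c in both arms, the difference is the true one times (1 - c): 30 × 0.70 = 21. That is dilution without reversal. Reversal needs (1 - c on placebo)/(1 - c on active) to fall below (1 - t on active)/(1 - t on placebo). For toxicity 40%/10% the limit is 0.60/0.90 = 0.667. With 10% CIDP worsening on active, the sign changes once placebo exceeds 1 - 0.667 × 0.90 = 40%.

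If the CIDP terms are excluded, each row returns to its true +15 or +30 points, provided the term list captures the CIDP events and nothing else.

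**The case against.** The strongest reply is that the rule restricts recording and that the SAP already shows toxicity in other ways. Most of the individual points stand.

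- A reader might infer that every relapse becomes an AE. The documents do not say so. The increase is judged against the subject's known history, and every participant has a documented decline on Ig reduction or withdrawal, so an investigator could regard a similar relapse as within that history. An adjusted INCAT relapse is only a 1-point rise. The withdrawals and missing Week 13 data that SAP 4.2.1 counts as relapse are not AEs at all.
- A reader might infer that all headline rows are affected. The related row needs a causality judgement and the deaths row a fatal outcome, so both are little exposed. Relapse or rescue is its own criterion for stopping IMP, the eCRF records a primary reason, and SAP 5.1 tabulates reasons for study discontinuation. A relapse stop therefore need not enter the discontinuation row.
- A reader might infer that toxicity would be hidden from the safety comparison as a whole. It would not. Headache, gastrointestinal, infusion-reaction and other named toxicities have their own tables by seriousness, relationship and intensity. CIDP terms appear at PT level, and relapse and rescue are summarized by arm. With about 34 participants, the listing would allow a count by hand.

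What remains is narrower. PT tables do not give participant-level totals across terms, and CIDP symptoms may be coded to several terms. A hand count from the listing would have its terms chosen after unblinding unless a list had been fixed. The AE-of-focus set has no group for CIDP worsening.

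**Conclusion.** The point holds for the pooled overview rows only: any, serious, Grade 3 and above, and discontinuation where the stop is attributed to an AE. Those rows can move with efficacy as well as toxicity, and an excess of recorded CIDP worsening on placebo would dilute or reverse a toxicity difference in them.

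The design makes such an excess plausible, but no document states a rate, so the size cannot be set. The +9 and -9 point results rest on assumed rates and on independence of the two kinds of event. They show that the mechanism works and are not a forecast. The reversal also requires that the worsening be recorded as AEs, and for the discontinuation row that the stops be attributed to them.

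Safety reporting is descriptive, and nothing makes the overview table the sole basis of the safety conclusion. This is a worthwhile low-cost improvement to the display and does not invalidate the safety analysis.

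**What to change.** In SAP 10.2, before unblinding, have staff blinded to arm fix a list of MedDRA preferred terms that represent CIDP worsening. Present the any, serious, Grade 3 and above and discontinuation overview rows by arm twice: for all TEAEs, and excluding the listed terms.

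Keep the all-TEAE rows as the primary display and read the two together. Listed terms such as weakness, pain or gait difficulty could also be drug effects, so the reduced rows must not replace the full ones.

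Build the exclusion on preferred terms alone. The documents describe a rescue flag on concomitant medication and an investigator field for other relapse, but no eCRF link from an AE to relapse or rescue. One sentence stating whether relapses that meet Protocol 12.1.1.1 are entered on the AE page would help readers interpret both versions.

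The cost is SAP wording, one blinded term list and one repeated overview table. No new data are needed. The downside is some judgement in choosing terms, which fixing the list under blind limits.

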### 10.3 Clinical laboratory evaluations

Laboratory data (chemistry, hematology and urinalysis) and changes from Baseline (if applicable) for numeric variables will be listed by treatment group and timepoint. Any laboratory measurements that are BLQ or ALQ will be handled as described in Section 4.2.2. Values outside the reference range for the numeric variables will be flagged in the listings. The reference ranges will also be reported in the listings. In addition, the listings will include a flag for values identified as markedly abnormal (MA) as defined by the criteria outlined in Section 13.2.

Chemistry and hematology parameters will be summarized by treatment group for both absolute values and changes from Baseline.

The laboratory variables to be included in the final analysis are presented in [Table 10-1](#).

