## **14.4 Other analyses**

### **14.4.1 Safety analyses**

The incidence of subjects with TEAEs will be determined by treatment group. Furthermore, the absolute and relative frequencies for subjects with a given TEAE with respect to the preferred term according to the latest available version of the Medical Dictionary for Regulatory Activities (MedDRA®), will be determined within each treatment group and system organ class. Additional tables will summarize TEAEs by maximum severity and causal relationship with rozanolixizumab, as judged by the investigator, per treatment group. Adverse events will be categorized by severity according to the National Institutes for Health (CTCAE) version 4.03 grading (National Institutes for Health, 2009). In case the CTCAE grading is not available, the intensity (mild/moderate/severe) will be utilized. The TEAEs leading to discontinuation of IMP and the serious TEAEs will also be summarized by treatment group. The action taken, time of onset relative to dosing, actual dose received, and duration of each AE will be listed only.

For the continuous laboratory variables, the values and changes from Baseline will be descriptively summarized by treatment group at each time point. For categorized values according to the reference range, shift tables from Baseline to each post-Baseline time point will be presented for selected variables to be defined in the SAP. Values outside the reference range will be flagged in the data listings.

Descriptive statistics will be presented for ECG value and changes from Baseline by treatment group and over time based on the mean of the triplicate assessments at each time point. Categorical analyses for QTc, eg, QTc increase >60msec, will also be performed.

Descriptive statistics will be reported for all vital sign measurements (including BP, PR, temperature, and body weight). Measured values and changes from Baseline will be summarized by treatment group and by time point.

Physical and neurological examination findings and the results of any pregnancy testing will be presented in listings only. Results will be listed for any subjects who complete a headache questionnaire, undergo stool sampling, or lumbar puncture, etc.

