#### 4.2.8 Handling of repeated and unscheduled measurements

All repeated and unscheduled measurements will be presented in the listings, where applicable. The following general rules will apply to all repeated and unscheduled measurements:

- For repeated or unscheduled measurements obtained prior to dosing the latest value (which may be scheduled or unscheduled) will be used in the calculation of the descriptive statistics at each visit (ie, Screening and/or Baseline);
- For repeated or unscheduled measurements obtained at the designated Baseline visit, the latest value (which may be scheduled or unscheduled) will be defined as the Baseline provided that the measurement occurred prior to dosing;
- For repeated or unscheduled measurements taken at any timepoint after dosing, the original values (if non-missing) will be used in the calculation of changes from Baseline and for the descriptive statistics (ie, in summaries by timepoint). Unscheduled and repeated measurements will generally not be included in the summaries by timepoint after dosing.

The above rules also apply to triplicate measurements obtained for the ECG data

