A listing will be presented by treatment group and participant for all AEs. This will include the onset date/time and outcome date/time of the event (including relative days), the AE duration, days since first dose of IMP, days since most recent dose of IMP, actual dose received, study period, pattern of event, severity/intensity, relationship, action taken and outcome. In addition, the listing will flag AEs that led to discontinuation, TEAEs, serious adverse events (SAEs), AEs of interest, AEs of special interest and infusion reactions.

AEs of focus (ie, TEAEs that are a review focus for rozanolixizumab or the participant population) will be summarized, in separate tables, detailing all TEAEs meeting the following criteria described below:

- Headache using the UCB-defined search criteria.
- Gastrointestinal disturbances using the UCB-defined search criteria.
- Hypersensitivity reactions using the criteria SMQ='Hypersensitivity'
- Anaphylactic reactions using the criteria SMQ='Anaphylactic reaction' and the UCB-defined search criteria.
- Injection site reactions using the UCB-defined search criteria.
- Infusion reaction collected on the eCRF AE page.
- Opportunistic infections using the UCB-defined search criteria.
- Reductions in albumin and plasma proteins using the UCB-defined search criteria.
- Effects on the kidney using the criteria SMQ='Acute renal failure'
- Drug related hepatic disorders using the criteria SMQ='Drug related hepatic disorders - comprehensive search'.

For each of the above-mentioned AEs of focus the following summaries will be presented:

- Incidence of all AEoFs by SOC, HLT and PT
- Incidence of all AEoFs by Relationship, SOC, HLT and PT
- Incidence of all serious AEoFs by SOC, HLT and PT
- Incidence of all AEoFs by Maximum Intensity, SOC, HLT and PT

UCB definitions for AEoF are found in a separate document "Adverse Events (AEs) of Focus for the rozanolixizumab Program" version 1.3, dated 04 Aug 2020.

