## 13.2 Marked abnormality criteria for Rozanolixizumab program

The following criteria will be applied in the determination of marked abnormalities for laboratory assessment values for the clinical studies within the Rozanolixizumab clinical development program. These values are based on the CTCAE criteria version 5, grade 3 or higher criteria unless otherwise noted.

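### The SAP leaves the protocol's laboratory shift tables undefined and uses its marked-abnormality criteria only as listing flags, so outside the liver table threshold-crossing laboratory values get no count by arm

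*SAP*

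**What the plan says.** The protocol makes two commitments in Section 14.4.1. The first is general: "For the continuous laboratory variables, the values and changes from Baseline will be descriptively summarized by treatment group at each time point". Urinalysis is not excluded. The second concerns values categorised against the reference range: "shift tables from Baseline to each post-Baseline time point will be presented for selected variables to be defined in the SAP".

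SAP 10.3 lists chemistry, hematology and urinalysis results, then limits its summary sentence to two of the three: "Chemistry and hematology parameters will be summarized by treatment group for both absolute values and changes from Baseline". For abnormal values it says "Values outside the reference range for the numeric variables will be flagged in the listings", and it adds an MA flag to the same listings. The MA thresholds are in SAP 13.2, introduced with "The following criteria will be applied in the determination of marked abnormalities for laboratory assessment values". SAP 10.4.1 treats the vital-sign thresholds of Table 10-2 in the same way, as a listing flag. No laboratory shift table is described and no variable is named for one.

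SAP 4.2.8 adds: "Unscheduled and repeated measurements will generally not be included in the summaries by timepoint after dosing".

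Other laboratory and ECG thresholds are counted. SAP 10.3.1 plans a table of participants meeting liver criteria at any visit, and SAP 10.4.2 gives numbers and percentages by arm for QTcF cut-points. SAP 10.2 plans adverse-event-of-focus tables, including "Reductions in albumin and plasma proteins using the UCB-defined search criteria" and effects on the kidney.

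**The concern.** Safety and tolerability are a secondary objective, and albumin and total protein are named safety variables in Protocol 4.2.6. Laboratory harm often appears as a few participants with marked changes rather than as a shift in the arm mean. The usual tools for showing this are shift tables and counts of participants beyond a threshold. The protocol promised the first, and the SAP has defined the thresholds for the second, yet SAP 10.3 specifies neither table.

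Unscheduled and repeat draws may be taken because something looked wrong, and these are the results generally left out of the by-visit summaries. Outside the liver, a marked abnormality found only at such a draw would appear as a flagged line in a listing. It would enter a comparison between arms only if the investigator reported it as an adverse event.

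**Working it through.** **1. Protocol against SAP**

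| Item | Protocol 14.4.1 | SAP |
|---|---|---|
| Shift tables | Promised; variables left to the SAP | 10.3 names none; 3.9 declares no change |
| Continuous summaries | All continuous laboratory variables, by arm and time point | 10.3 mentions chemistry and hematology only |
| Quantitative urine albumin, creatinine, protein | Not excluded | In Table 10-1 and listed; no summary stated in 10.3, although 4.2.2 applies its descriptive-statistics rules to urinalysis |
| Out-of-range values | Flagged in listings | Flagged in listings |
| MA thresholds | None | 13.2 and Table 10-2, as listing flags only |

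**2. What each planned output does with a value beyond an MA limit**

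- Scheduled visit: it enters the by-visit mean, SD, median, minimum and maximum (SAP 3.1). The minimum or maximum can show the most extreme value, not how many participants crossed the limit.
- Unscheduled or repeat draw after dosing: generally excluded from by-visit summaries (SAP 4.2.8).
- Liver parameters: counted at any visit (SAP 10.3.1).
- Total IgG: each participant's minimum and maximum decrease are derived from all available data and summarised by arm (SAP 9.2.1).
- Reported as a TEAE: counted by arm (SAP 10.2). Protocol 12.1.1.1 allows an abnormal laboratory finding to be an adverse event, but outside liver injury I found no rule that a threshold-crossing value must be reported as one. Protocol 7.8.1.1 also withholds potentially unblinding laboratory results from sites, without saying which.

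**3. Participants per arm**

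SAP 2.4 gives 15 evaluable per arm, 10% not evaluable and 34 randomized. 2 × 15 / 0.90 = 33.3, rounded up to 34, which reproduces the plan's figure. With 1:1 allocation this is 34 / 2 = 17 per arm.

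**4. Illustration with albumin**

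The documents give no albumin distribution, so the falls and baselines here are assumptions.

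- One participant falling by 20 g/L: 20 / 17 = 1.18 g/L change in the arm mean.
- The MA limit is below 20 g/L, so a 20 g/L fall meets it only if baseline is below 40 g/L.
- One participant falling to 19 g/L, just inside the criterion, from 40 g/L: (40 − 19) / 17 = 1.24 g/L. For baselines of 35 to 45 g/L the range is 0.94 to 1.53 g/L.
- Two such participants from 40 g/L: 2 × 21 / 17 = 2.47 g/L (1.88 to 3.06 g/L).
- If the value is seen only at an excluded unscheduled draw, the by-visit mean moves by 0.
- In a count table: 1/17 = 5.9% (exact 95% CI 0.1 to 28.7%); 2/17 = 11.8% (1.5 to 36.4%).

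**5. Suppression of by-visit statistics**

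SAP 4.2.2 gives no descriptive statistics at a time point where more than 33% of values are missing or unquantifiable. The denominator is not stated. If it is the arm, 5/17 (29.4%) keeps the statistics and 6/17 (35.3%) removes them, including the minimum and maximum.

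**The case against.** A reader might infer three stronger things, and the documents do not support them.

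- *That albumin, kidney and blood-count harms get no between-arm count at all.* SAP 10.2 plans adverse-event-of-focus tables for albumin and plasma proteins and for the kidney, also by relationship, seriousness and maximum intensity. All TEAEs, including reported blood-count events, are tabulated by system organ class, high level term and preferred term. Section 10 makes these tabulations by treatment group. What is missing is a count based on the laboratory values.
- *That the SAP cancelled the protocol's analyses.* SAP Section 1 keeps the protocol's analysis in force unless the SAP specifies otherwise, and SAP 10.3 does not revoke the shift tables or forbid a urinalysis summary. This stands for urinalysis, where the gap is one of clarity. It does not rescue the shift tables, because the protocol leaves the choice of variables to the SAP.
- *That a scheduled outlier would be invisible.* By-visit minima and maxima, for both values and changes, would usually show it, and total IgG has its own worst-value summary.

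It can also be said that neither document promises MA counts and that the protocol itself asks only for listing flags on out-of-range values. In a 34-participant exploratory trial the flagged listings by arm can be counted by hand, and the interim patient profiles of SAP 11 show individual laboratory courses for the unblinded monitoring committee. All true. The MA table is therefore an improvement, not an unmet promise. But a hand count from listings is not a prespecified comparison, and the profiles serve the interim reviews.

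**Conclusion.** The point holds in a limited form. The protocol's shift tables cannot be produced from the SAP as written, because no variables are named, and SAP 3.9 does not record this. The urinalysis summary is unclear: SAP 10.3 omits it while SAP 4.2.2 assumes it. Outside the liver table and the total IgG summary, values crossing the SAP's own limits have no laboratory-value-based count by arm, and those found only at unscheduled draws generally enter no by-visit summary.

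The size is a matter of visibility and does not touch sample size or power. At 17 per arm one affected participant is 1/17 (5.9%) in a count table, against a shift of about 1.2 g/L in mean albumin if the assumed fall is at a scheduled visit, and 0 if it is not. The albumin figures rest on assumed baselines, and the 20 g/L fall meets the MA criterion only from a baseline below 40 g/L. With intervals as wide as 0.1 to 28.7%, the added tables would describe harms, not test them.

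**What to change.** 1. **SAP 10.3, shift tables.** Name the variables, for example albumin, total protein, creatinine, neutrophils, lymphocytes, platelets and hemoglobin.
2. **SAP 10.3 and 10.4.1, MA counts.** Add a table of n (%) by arm of participants with at least one post-Baseline MA value, for each Section 13.2 parameter actually collected and each Table 10-2 criterion, using scheduled and unscheduled results. Estimated GFR and serum glucose have limits in Section 13.2 but are not in the planned chemistry panel (SAP Table 10-1, Protocol Table 12-3), so leave them out unless their source is defined. This table is what brings in the unscheduled draws; by-visit shift tables under SAP 4.2.8 would not.
3. **SAP 10.3, urinalysis.** State that quantitative urine albumin, creatinine and protein are summarised by arm and visit, as Protocol 14.4.1 requires.
4. **SAP 3.9.** Record and justify whichever protocol commitment is not kept.

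The cost is some SAP wording and a few extra tables, from data and thresholds already in the plan. Ratios of urine albumin or protein to creatinine would be an optional refinement; neither document calls for them.
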